1. INTRODUCTION AND BACKGROUND

Johnson & Johnson Vision (JJV) recently launched a multifocal contact lens, 1-DAY ACUVUE® Moist Multifocal. The lens is the only marketed soft multifocal lens to have its optical design optimized for the changes that occur in pupil size with refractive error. The modality for the lens is daily disposable. There is a desire to evaluate the same optical design in a reusable modality. The purpose of this study is to evaluate a multifocal optical design manufactured from senofilcon A material and compare the visual performance to the 1-DAY ACUVUE® Moist Multifocal.

1.1. Name and Descriptions of Investigational Products

Test Lens: JJV Investigational senofilcon A Multifocal Contact Lens-The lens has the same optical design, diameter, aspheric back surface design as the 1-Day Acuvue® Moist Brand Multifocal. The lens is manufactured in senofilcon A.

Control Lens: Marketed 1-Day Acuvue® Moist Brand Multifocal Contact Lenses

1.2. Intended Use of Investigational Products

Both lenses are intended to correct spherical refractive error and presbyopia. The Test lenses are intended to be used as a 2-week, reusable, daily wear lens. The lenses require use of a care system to clean and disinfect the lenses. The control lenses are daily wear lenses that are disposed of at the end of each wear cycle. No care system is required for the control lenses.

1.3. Summary of Findings from Nonclinical Studies

All previous pre-clinical findings were deemed satisfactory prior to proceeding with clinical trials on humans. For the most comprehensive nonclinical information regarding JJV investigational senofilcon A multifocal refer to the latest version of the Investigator Brochure.

1.4. Summary of Known Risks and Benefits to Human Subjects

The Investigational multifocal contact lenses are designed as a continuous asphere providing for the correction of refractive spherical ammetropia and presbyopia. The material is a silicone hydrogel material, senofilcon A.

The 1-Day Acuvue® Moist Brand Multifocal Contact Lens is a currently marketed product that is made of the etafilcon-A material. The contact lenses are available as continuous aspheres providing for the correction of a subjects refractive spherical ammetropia and presbyopia.

The intent of the Test lens is daily wear, reusable lens that the subject wears while awake. This lens is not intended for extended wear. Anticipated risks and adverse reactions with this lens are similar to other soft daily wear contact lenses used to correct presbyopia. A listing of examples of adverse reactions is found in the Section 13 of this protocol. The investigator should follow normal clinical guidelines regarding examination and care of subjects who participate in this trial. For the most comprehensive clinical information regarding the JJV Investigational senofilcon A multifocal lens refer to the Investigator Brochure. Additional

Clinical Study Protocol

Johnson & Johnson Vision Care, Inc.

details on the 1-Day Acuvue® Moist Brand Multifocal Contact Lens can be found in the package insert in Appendix C.

1.5. Relevant Literature References and Prior Clinical Data Relevant to Proposed Clinical Study

JJV has evaluated the test lenses in the previous clinical studies: [REDACTED]

[REDACTED] A summary of these studies is listed below.

[REDACTED] was a dispensing clinical trial with primary end points of logMAR visual acuity at fit and CLUE vision scores at 1 week. The study was a cross-over design with a marketed product serving as the control. There were 32 subjects that completed the study as cohort. The Test lens displayed good visual acuity with the mean distance and intermediate logMAR acuity better than 0.0 and the mean near logMAR acuity better than +0.1 logMAR. This with true of the acuity at the initial fit as well as the 1 week and 2-week visits in the final lens pair. There were two non-ocular adverse events that occurred during the study that were not related to any of the Test lenses.

[REDACTED] was a dispensing parallel-ARM study and had a primary endpoint of logMAR visual acuity. There were 149 subjects that completed the study overall with 37 subjects completing in the ARM involving the study lenses that will be used in this study. The lenses displayed clinically acceptable logMAR visual acuity after approximately 2 weeks of wear with the mean bright high contrast binocular logMAR acuity of -0.077, -0.083 and 0.049 for distance, intermediate and near respectively.

[REDACTED] had four parallel ARMs with one of the ARMs being the test lenses evaluated in this study along with two other investigational test lenses and a control lens. For the ARM with the lenses tested in this study there were no ocular adverse events reported and one non-ocular that was not related to the test article.

[REDACTED] was a dispensing crossover study on myope subjects and had a primary endpoint of subject vision response. There were 53 subjects that completed the study as cohort. The test lenses displayed clinically acceptable logMAR visual acuity after approximately 2 weeks of wear with the mean bright high contrast binocular logMAR acuity of -0.11, -0.07 and 0.06 for distance, intermediate and near respectively. There was one adverse event in the study that was a non-significant temporal conjunctival hyperemia in the right eye after removal of their lenses. The event resolved without any treatment.

[REDACTED] was a dispensing crossover study on hyperope subjects and had a primary endpoint of subject vision response. There were 59 subjects that completed the study as cohort. The test lenses displayed clinically acceptable logMAR visual acuity after approximately 2 weeks of wear with the mean bright high contrast binocular logMAR acuity of -0.05, -0.02 and 0.11 for distance, intermediate and near respectively. One subject had a non-ocular serious adverse event of dehydration of moderate severity and received treatment for this event. Although the event was reported as resolved, the subject was permanently discontinued the study. The investigator considered the event to be not related to the study article/study procedure. Three episodes of ocular adverse events were reported. One subject had an ocular AE of non-

Clinical Study Protocol

Johnson & Johnson Vision Care, Inc.

significant corneal foreign body of mild severity. The subject did not receive any treatment for this event. The event of non-significant corneal foreign body was reported as resolved and no action was taken with the study article. The investigator considered the event to be not related to the study article/study procedure. A second subject had two episodes (one in each eye) of significant infiltrative event (SIE) of moderate severity. The subject received treatment for these events. Although the events were reported as resolved, the subject was permanently discontinued the study. The investigator considered the events to be related to the study article/study procedure.

████████ was a dispensing crossover study on hyperope subjects and had a primary endpoint of subject vision response. There were 42 subjects that completed the study as cohort. The test lenses displayed clinically acceptable logMAR visual acuity after approximately 2 weeks of wear with the mean bright high contrast binocular logMAR acuity of -0.025, -0.045 and 0.173 for distance, intermediate and near respectively. There was one adverse event in the study that was a non-significant contact lens acute red eye in the right eye. The event was classified as related to the test article and resolved with treatment.

In addition to the above studies, JJV had tested similar optical designs that have been manufactured in a similar material, however those lenses were worn as daily disposable lenses. The lenses were tested in ██████████ Additional details regarding these studies can be found in the ██████████ Investigator Brochure.

2. STUDY OBJECTIVES, ENDPOINTS AND HYPOTHESES

2.1. Objectives

This primary objective of this pilot study is to evaluate the visual performance of the JJV Investigational senofilcon A Multifocal Contact Lens (Test) made using a new manufacturing process by comparison with 1-Day Acuvue® Moist Brand Multifocal (Control).

The secondary objective is to evaluate the clinical performance of the Test lens by comparisons with the control lens in the following areas:

- Vision (subjective)
- Comfort
- Slit Lamp Findings
- Patients' reported ocular symptoms

2.2. Endpoints

Primary Endpoint(s)

The primary endpoint is contact lens-corrected visual performance on logMAR scale. This will be evaluated binocularly under high luminance high contrast, Dim luminance high contrast and high luminance low contrast conditions at 4 meters (distance), 64 cm (intermediate) and 40 cm (near) from ETDRS/reduced Guillon-Poling charts at the 2-week follow-up visit. For more details refer to section 7.2 Detailed Study Procedures.

Clinical Study Protocol

Johnson & Johnson Vision Care, Inc.

Secondary Endpoints:

- Overall quality of vision scores on CLUE scale
- Overall comfort scores on CLUE scale
- Subject reported ocular symptoms
- Slit Lamp Findings

Other Endpoints(s)

- Lens fitting characteristics (lens centration, lens movement, overall lens fitting acceptability)
- Average daily wear time (in Hours)
- Corneal staining
- Ocular redness (bulbar and limbal)
- Summary of number of lenses needed to fit (optimize) the subject
- Lens deposits
- Overall handling scores on CLUE scale
- Product performance survey questionnaire

Adverse events, number and reasons for discontinuation, number and reasons for unscheduled lens replacement including lens damage will be monitored and descriptively evaluated.

CLUE™ is a validated patient reported outcomes (PRO) questionnaire to assess patient-experience attributes of soft contact lenses (comfort, vision, handling, and packaging) in a contact-lens wearing population in the US, ages 18-65. Derived CLUE™ scores using Item Response Theory (IRT) follow a normal distribution with a population average score of 60 (SD 20), where higher scores indicate a more favorable/positive response with a range of 0-120. A 5-point increase in an average CLUE™ score translates into 10% shift in the distribution of scores for population of soft contact lens wearers.⁷

2.3. Hypotheses

Primary Hypotheses:

The Test lens will be non-inferior to the Control lens with respect to binocular contact lens-corrected visual performance at near, intermediate and distance under high luminance high contrast, Dim luminance high contrast and high luminance low contrast conditions. A non-inferiority margin of 0.05 on logMAR scale will be used.

Secondary Hypotheses:

No secondary hypotheses will be tested. All secondary endpoints will be evaluated with summary tables (see Section 14 for more details). The following will be calculated:

- Average (SD) comfort scores on CLUE scale by study lens at each follow-up visit
- Proportion of eyes with clinically significant (Grade 3 or 4) slit lamp findings.
- Proportion of eyes with reported ocular symptoms.

Clinical Study Protocol

Johnson & Johnson Vision Care, Inc.

3. TARGETED STUDY POPULATION

3.1. General Characteristics

Healthy male and female subjects who are habitual soft contact lens wearers will be recruited. Subjects will be at least 40 years of age and not older than 70 years of age. They will be hyperopic and have presbyopia.

3.2. Inclusion Criteria

Potential subjects must satisfy all of the following criteria to be enrolled in the study:

Inclusion Criteria after Screening:

1. The subject must read, understand, and sign the STATEMENT OF INFORMED CONSENT and receive a fully executed copy of the form.
2. The subject must appear able and willing to adhere to the instructions set forth in this clinical protocol.
3. The subject must be at least 40 years of age and not greater than 70 years of age at the time of consent.
4. Subjects must own a wearable pair of spectacles if required for their distance vision.
5. The subject must be an adapted soft contact lens wearer in both eyes (i.e. worn lenses a minimum of 2 days per week for at least 8 hours per wear day, for 1 month or more duration).
6. The subject must either already be wearing a presbyopic contact lens correction (e.g., reading spectacles over contact lenses, multifocal or monovision contact lenses, etc.) or if not respond positively to at least one symptom on the “Presbyopic Symptoms Questionnaire” (Appendix E).

Inclusion Criteria after Baseline:

7. The subject’s distance spherical equivalent refraction must be in the range of +1.25 D to +3.75 D in each eye.
8. The subject’s refractive cylinder must be ≤ 0.75 D in each eye.
9. The subject’s ADD power must be in the range of +0.75 D to +2.50 D.
10. The subject must have distance best corrected visual acuity of 20/20⁻³ or better in each eye.

3.3. Exclusion Criteria

Potential subjects who meet any of the following criteria will be excluded from participating in the study:

Exclusion Criteria after Screening:

1. Currently pregnant or lactating.
2. Any active or ongoing ocular or systemic allergies that may interfere with contact lens wear.

Clinical Study Protocol

Johnson & Johnson Vision Care, Inc.

3. Any active or ongoing systemic disease, autoimmune disease, or use of medication, which may interfere with contact lens wear. This may include, but not be limited to, diabetes, hyperthyroidism, Sjögren's syndrome, xerophthalmia, acne rosacea, Stevens-Johnson syndrome, and immunosuppressive diseases or any infectious diseases (e.g. hepatitis, tuberculosis).
4. Any previous, or planned, ocular or intraocular surgery (e.g. radial keratotomy, PRK, LASIK, lid procedures, cataract surgery, retinal surgery, etc.).
5. A history of amblyopia, strabismus or binocular vision abnormality.
6. Use of any of the following medications within 1 week prior to enrollment: oral retinoid isotretinoin (e.g. Accutane), oral tetracyclines, oral phenothiazines, oral/topical/inhaled anticholinergics, systemic/topical corticosteroids.
7. Use of any ocular medication, with the exception of rewetting drops.
8. History of herpetic keratitis.
9. History of irregular cornea.
10. History of pathological dry eye.
11. Participation in any contact lens or lens care product clinical trial within 30 days prior to study enrollment.
12. Employee or immediate family member of an employee of clinical site (e.g., Investigator, Coordinator, Technician).
13. Any known hypersensitivity or allergic reaction to Optifree® Replenish® multi-purpose care solution, sodium fluorescein or non-preserved rewetting drop solutions.

Exclusion Criteria after Baseline:

14. Clinically significant (Grade 2 or greater) corneal edema, corneal vascularization, corneal staining, tarsal abnormalities or bulbar injection, or any other corneal or ocular abnormalities which would contraindicate contact lens wear.
15. Entropion, ectropion, extrusions, chalazia, recurrent styes, glaucoma, history of recurrent corneal erosions.
16. Any current ocular infection or inflammation.
17. Any current ocular abnormality that may interfere with contact lens wear.

3.4. Enrollment Strategy

Study subjects will be recruited from the Institution/clinical site's subject database and/or utilizing Independent Ethics Committee (IEC) or Institutional Review Board (IRB) approved materials.

4. STUDY DESIGN AND RATIONALE

4.1. Description of Study Design

The clinical study is a randomized-controlled, single-masked, cross-over clinical trial. There are two study lenses. Each lens will be dispensed for 3 ± 1 days and an optimization visit will occur. The final lens pair will be dispensed for 12 ± 2 days and the follow-up on the final lens pair will occur. The second study lenses will then be fit and the above sequence repeated.

Clinical Study Protocol

Johnson & Johnson Vision Care, Inc.

4.2. Study Design Rationale

The study is intended to compare two study lens types and the initial performance, in terms of the subjective response after a period of lens dispensing. The lenses are dispensed to determine the subjective responses and the comparison is made after a total of 14-20 days of wear.

The cross-over study design was chosen to control for variables that may impact the lens performance between subjects. A washout period will be used to minimize the chances of a significant carry over effect impacting the primary/secondary endpoints measured in the study.

4.3. Enrollment Target and Study Duration

Up to 48 eligible subjects will be enrolled with 40 targeted to complete the study. The anticipated study duration is approximately 3 months.

5. TEST ARTICLE ALLOCATION AND MASKING

5.1. Test Article Allocation

The study lenses will be worn in a bilateral and random fashion using a 2×2 crossover design with 2 lens types and 2 periods. Using a computer-generated randomization scheme provided by the study biostatistician, each subject will randomly be assigned to one of two unique sequences (Test/Control or Control/Test). Randomization will be stratified by site.

Permuted block randomization will be used to avoid bias in the assignment of subjects to treatment, and to enhance the validity of statistical comparisons across treatment groups. Each block will contain two different lens trial sequences.

Randomization must be performed at the initial visit. The following must have occurred prior to randomization:

- Informed consent has been obtained
- It has been determined that the subject meets all the inclusion / exclusion criteria
- Subject history and baseline information has been collected

The order of lens wear will be based on the randomization scheme assigned to the study site. The study site will follow the randomization scheme provided and will complete enrollment according to the randomization list and will not pre-select or assign subjects.

5.2. Masking

This is a single-masked (partial) study with the subjects being masked. Subjects will be aware that there are differences in modalities between lens types however they will not be told anything regarding the optical design other than the design is intended to correct for their spherical refractive error and presbyopia. Subjects will be unaware of the identity of the assigned investigational products. Investigators and clinical site personnel involved in the data collection will be aware of the identity of the assigned investigational products.

Clinical Study Protocol

Johnson & Johnson Vision Care, Inc.

The identity of the study lenses will be masked to subjects by over labeling the blister packs with a label containing the study number, lot number, sphere power, add power, expiration date and the randomization codes. Investigators and medical monitor will have access to the decode information translating the randomization codes into Test and Control arms.

Under normal circumstances the mask should not be broken until all subjects have completed the study and the database is finalized. Otherwise, the mask should be broken only if specific emergency treatment/course of action would be dictated by knowing the treatment status of the subject. In such cases, the Investigator may, in an emergency, contact the medical monitor. In the event the mask is broken, the Sponsor must be informed as soon as possible. The date, time, and reason for the unmasking must be documented in the subject record. The Investigator is also advised not to reveal the study treatment assignment to the clinical site or Sponsor personnel.

Subjects who have had their treatment assignment unmasked are expected to return for all remaining scheduled evaluations. Subjects who are discontinued may be replaced.

5.3. Procedures for Maintaining and Breaking the Masking

The test articles mask shall not be broken unless information concerning the lens type is necessary for the urgent medical treatment of a subject. The Sponsor must be notified before the mask is broken.

When dispensing test articles, the following steps should be followed to maintain randomization codes:

1. Investigator or designee (documented on the Delegation Log) will consult the lens fitting schedule/randomization scheme to obtain the test article assignment for that subject prior to dispensing
2. Investigator or designee will record the subject's number on the appropriate line of the randomization scheme if applicable
3. Investigator or designee will pull the appropriate test articles from the study supply. All test articles that are opened, whether dispensed (placed/fit on eye or dispensed outside the clinical site) or not, must be recorded on the Test Article Accountability Log in the "Dispensed" section

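### Sections 5.1 to 5.3 have unmasked investigators, who hold the decode, take assignments from a list used at the site in small site-stratified blocks and describe no concealment, so upcoming sequences can be known before eligibility is decided

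*Combined protocol and SAP*

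**What the plan says.** Section 5.1 has the study biostatistician supply a computer-generated scheme, stratified by site, with two sequences (Test/Control and Control/Test). On blocking: "Each block will contain two different lens trial sequences". On its use: "The study site will follow the randomization scheme provided and will complete enrollment according to the randomization list". Consent, a completed eligibility decision and baseline data must come before randomization, and the site is told not to pre-select or assign subjects.

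Section 5.2 masks subjects only. "Investigators and clinical site personnel involved in the data collection will be aware of the identity of the assigned investigational products". Also: "Investigators and medical monitor will have access to the decode information translating the randomization codes into Test and Control arms".

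Section 5.3, describing dispensing, says that the investigator or designee "will consult the lens fitting schedule/randomization scheme to obtain the test article assignment for that subject prior to dispensing", and then records the subject's "number on the appropriate line of the randomization scheme if applicable".

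In Section 7.2, eligibility is settled at steps 1.7 and 1.19, and the randomization ID is recorded at step 1.20. The reference beside step 1.20 is redacted.

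**The concern.** Random allocation protects a trial only if the person deciding on entry cannot tell what the next subject will receive. Here the people who judge eligibility work from the list, know the lenses and hold the key to the codes. Several entry criteria need judgement: inclusion 2 (whether the subject seems able and willing to comply) and exclusions 2, 3 and 17 (conditions that might interfere with lens wear). The stated safeguards are an order of events and a prohibition. Neither hides an assignment that is already on paper at the site.

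At stake is a non-inferiority conclusion against a 0.05 logMAR margin, where a bias favouring Test makes a false claim more likely. The crossover limits the damage, because each completer wears both lenses. Two routes remain. Subjects whose acuity shifts between periods could be placed mainly in one sequence; inclusion 6 admits both current multifocal wearers and people with no presbyopic lens correction, so such types are plausible. And subjects likely to leave on the first lens could be placed mainly in one sequence, which matters because the primary analysis uses per-protocol completers (Sections 14.3 and 14.5).

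**Working it through.** **1. What can be known in advance.**
- List open at the site, with the decode: up to 48 of 48 assignments.
- List hidden, known blocks of two: the second place in each block follows from the first. Certain: 1/2, or 24 of 48. Correct guesses: (0.5 + 1)/2 = 75%.
- List hidden, known blocks of four: place 4 is always certain, and place 3 is certain when the first two match (probability 1/3). Certain: (1 + 1/3)/4 = 33.3%, or 16 of 48. Correct guesses: (1/2 + 2/3 + 2/3 + 1)/4 = 70.8%.
- The same enumeration gives 25% and 68.3% for blocks of six, and 20% and 66.6% for blocks of eight.
- Simple randomization: none certain, 50% guessed.

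The hidden-list figures assume complete blocks of a fixed size known to the site.

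**2. Reproducing the plan's own figures.** Inputs are the SDs and ICCs of Table 5, the 0.05 margin, a true difference of 0, 90% power and 2.5% one-sided alpha. The SD of a paired difference is √(s₁² + s₂² − 2·ICC·s₁·s₂).
- Smallest (distance, high luminance low contrast): √(0.091² + 0.105² − 2·0.68·0.091·0.105) = 0.0794.
- Largest (near, high luminance low contrast): √(0.103² + 0.130² − 2·0.69·0.103·0.130) = 0.0950.

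The paired t calculation with the noncentral t returns 29 and 40 for these rows, and all nine Table 5 sample sizes reproduce exactly. At 40 pairs the standard error runs from 0.0794/√40 = 0.0126 to 0.0950/√40 = 0.0150.

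**3. How steering becomes bias.** In a 2×2 crossover the bias in Test minus Control is half the between-sequence difference in mean period change. If one subject type changes by c between periods and its share differs by d between sequences, the size of the bias is 0.5·d·c. The values of c and d below are assumptions; the documents give neither.
- c = 0.02, d = 0.25: bias 0.0025.
- c = 0.04, d = 0.25: bias 0.005.
- c = 0.04, d = 0.50 (shares of 75% and 25%): bias 0.01.

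**4. False non-inferiority rate per endpoint.** The true difference is set at 0.05 and the bias favours Test. The rate is the chance that the upper two-sided 95% limit falls below 0.05, from the noncentral t with 39 df. This stands in for the credible interval of Section 14.5 under its vague priors. Ranges run over the nine Table 5 rows.

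| Assumed bias (logMAR) | False non-inferiority rate |
|---|---|
| 0 (no steering) | 2.5% |
| 0.0025 | 3.6–3.9% |
| 0.005 | 5.1–5.8% |
| 0.01 | 9.5–11.8% |

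**5. How much steering that takes.** Suppose the changing type is half of eligible candidates (an assumption). For shares of 75% and 25%, a site must turn away two-thirds of the unwanted type on each line: 0.5/(0.5 + 0.5/3) = 0.75. It then accepts 0.5 + 0.5/3 = 2/3 of candidates, so 48/(2/3) = 72 eligible people are needed to enrol 48. That makes the last row of the table an extreme case.

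**The case against.** The strongest reply is that the documents never say that future lines are visible. The Section 5.3 step belongs to dispensing and concerns a subject already in hand; it refers to the appropriate line, not the next one, and adds that this applies only where relevant. Randomization must follow the eligibility decision, and the redacted reference at step 1.20 could hold a release procedure. This stands against the reading that the next sequence is known or that allocation is demonstrably open. The text supports only that it can be known, because no concealment is described. The order-of-events rule does not answer that narrower point.

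Blocks of two are the plain reading but not the only one: the sentence also fits larger blocks containing both sequences. That too stands, so the 50% and 75% figures are conditional. The point survives, because list and decode alone are enough for it, and known blocks of four to eight still leave 33% to 20% of assignments certain.

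A reader might also infer that the sequence term in the Section 14.5 model carries the bias. It does not: with complete pairs it absorbs between-sequence differences in level, which then stay out of Test minus Control. Incomplete pairs enter only the ITT sensitivity analysis. Likewise, dropout on the first lens can differ by lens under perfect concealment, since staff are unmasked by design; concealment removes only the steering of likely dropouts into one sequence.

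Finally, a reader might take 9.5–11.8% as the expected error rate. The documents do not support that. It needs a 0.04 logMAR period change in one type, correct prediction of who will change, and consistent refusals on the scale of step 5. All subjects are adapted lens wearers, most baseline criteria are measured, and acuity is taken 12±2 days after the optimization visit.

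**Conclusion.** The concern holds in limited form. As written, Sections 5.1 to 5.3 combine a list used at the site, unmasked staff, access to the decode and small site-stratified blocks, with no described mechanism to hide upcoming sequences. Foreknowledge before eligibility is decided is therefore possible: up to 100% with an open list, or 50% certain with a hidden list and known blocks of two.

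The consequence is modest and its size is unknown. Assumed biases of 0.0025 to 0.005 logMAR, one-twentieth to one-tenth of the margin, would raise the one-sided false non-inferiority rate per endpoint from 2.5% to about 3.6–5.8%. Those rates rest on the Table 5 SDs and ICCs, 40 completed pairs and a paired t approximation. Without steering the rate stays at 2.5%, and nothing in the documents suggests that steering will occur. The case for changing the plan is that concealment is cheap to add now and cannot be restored after enrolment.

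**What to change.** In Sections 5.1 and 5.3, replace the list used at the site with release of one assignment at a time, only after the step 1.19 eligibility form is completed. The biostatistician keeps the list. Use the EDC system if it supports release; Section 15.1 documents it for data capture only, so otherwise use sequentially numbered, opaque, sealed envelopes opened after step 1.19. Delete the instructions to consult the scheme and to enter subjects on its lines.

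Replace the block sentence with site-stratified blocks of randomly varying size (for example 2, 4 and 6), with sizes not disclosed to sites. In Section 5.2, limit the investigator's decode to subjects already randomized.

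If a release procedure already exists behind the redacted references, align Sections 5.1 to 5.3 with it and still change the block scheme.

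The cost is a small set-up effort for EDC release or envelopes, with no extra subjects or visits. Stopping mid-block could leave an imbalance of up to 3 between sequences at a site, against at most 1 with blocks of two; the sequence, period and site terms already in the Section 14.5 model accommodate this.
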